8.6. Recording AEs and SAEs

Severity of AEs will be assessed according to CTC-AE Classification Version 5.0.

Patients will be asked to report all AEs as part of the procedures performed at each study visit. The site personnel will document all AEs in the patient's medical record. All AEs subsequently must be recorded in the appropriate eCRF sections.

The following points must be recorded for each event:

- A description of the event in medical terms, not as reported by the patient,
- Date of onset (start date),
- Date of resolution (stop date),
- The time of onset with respect to administering the investigational product,
- The severity of the sign/symptom or clinically significant abnormal laboratory value according to CTC-AE Classification (Most recent version),
- The causal relationship between the investigational product and the occurrence of each AE. This will be assessed by each investigator using clinical judgment. Alternative causes, such as natural history of the underlying diseases, concomitant medications, other risk factors and the temporal relationship of the event to the investigational product will have to be considered. The causality of all AEs should be assessed by the investigator with the following question: Is there a reasonable possibility that the AE may have been caused by the investigational product? And answered "NO" (if not related) and "YES" (if related);

- Action taken regarding the investigational product:
 - No action;
 - Temporary discontinuation;
 - Permanent discontinuation;
 - Patient's outcome:
 - Recovered without sequelae / resolved without sequelae;
 - Recovered with sequelae / resolved with sequelae;
 - Recovering/Resolving;
 - On-going;
 - Fatal (for SAEs only).

If in any one patient, the same AE occurs on several occasions, the AE in question must be documented and assessed anew each time.

8.7. Reporting of SAEs to ABIVAX or its designee

Throughout the study, the reporting of SAEs to the Sponsor or its designee will be done through the SAE forms.

It is the investigator's responsibility to ensure that the SAE report is submitted to IntuVigilance Limited **within 24 hours after knowledge of the event(s)**.

The study specific SAE form should be completed as thoroughly as possible, with all the available details of the event and signed by the investigator or designee. The investigator will assess causality between the study drug and the adverse event (AE) / serious adverse event (SAE) according to the table outlined below:

Related	A clinical event, including laboratory test abnormality, occurs in a plausible time relationship to treatment administration, and which concurrent disease or other drugs or chemicals cannot explain.
Probably related	A clinical event, including laboratory test abnormality, with a reasonable time sequence to administration of the treatment, unlikely to be attributed to concurrent disease or other drugs or chemicals.
Possibly related	A clinical event, including laboratory test abnormality, with a reasonable time sequence to administration of the treatment, but which could also be explained by concurrent disease or other drugs or chemicals.
Unlikely to be related	A clinical event, including laboratory test abnormality, with a temporal relationship to treatment administration which makes a causal relationship improbable, and in which other drugs, chemicals or underlying disease provide plausible explanations.
Unrelated	A clinical event, including laboratory test abnormality, with little or no temporal relationship with treatment administration. Typically explained by extraneous factors (e.g., concomitant disease, environmental factors or other drugs or chemicals).

An assessment of causality should always be provided at the time of the initial report. If the investigator or designee does not have all information regarding the SAE, he/she should not wait to receive additional information before completing the form and notifying IntuVigilance Limited.

Additional or follow-up information relating to the initial SAE report, will be requested, if necessary. Again, this information is to be completed and submitted through the SAE forms within 24 hours of receipt of the information.

In the rare occasion when the facsimile equipment does not work and in the absence of, the investigator should notify IntuVigilance Limited by telephone within the given timeframe and send a copy of the SAE report form by email.

8.8. Reporting of SAEs to Regulatory Authorities

ABIVAX has a legal responsibility to notify, as appropriate, both the local regulatory authorities and other regulatory agencies about the safety of the investigational medicinal product. It is therefore important that the investigator notifies promptly (within 24 hours) ABIVAX or designee of any SAEs, in order for legal obligations and ethical responsibilities towards other patients to be met.

In addition, the investigator or designee, will comply with the local regulatory requirements (when applicable) in reporting of SAEs to the ethics committee and, if required, to the relevant government authority.

Safety reports on adverse events that are serious AND unexpected AND causally associated with the investigational product are prepared according to ABIVAX's policy and applicable regulations and are forwarded to the investigators. These reports are filed with the investigator brochure or other appropriate study documentation. It is the Sponsor or its designee and/or investigator's responsibility to notify the IRB or IEC of these reports, if applicable according to local requirements.

9. DATA ANALYSIS AND STATISTICAL CONSIDERATIONS

A summary of the principal features of the statistical analysis of the data are described in this section. A more technical and detailed elaboration of the principal features stated in the protocol will be given in the statistical analysis plan (SAP).

Any amendments to the SAP will be clearly documented and signed prior to the final database lock including justifications and details of their potential impact on the interpretation of the study results.

9.1. Statistical and Analytical Plans

9.1.1. Protocol deviations

Protocol deviations will be reviewed and classed as major or minor during the blind-review meeting. Major protocol deviations are defined as deviations liable to bias the evaluation of the primary efficacy endpoint. The following deviations will be considered as major (non-exhaustive list):

- Non compliance with the inclusion or exclusion criteria;
- Non compliance with the study treatment;
- Intake of prohibited medication (see section 6.9.2);
- Noncompliance with time window.

9.1.2. Definition of study analysis sets

The following datasets will be defined and used for the analyses:

- Enrolled Analysis Set: All patients enrolled in the study will comprise of enrolled analysis set. There will be no safety or efficacy analysis performed on this set.
- Safety Analysis Set: The Safety analysis set will include all the patients randomized in the study and who have received at least one dose of study medication. The safety analysis will be based on the actual treatment received.
- The Full Analysis Set: FAS is defined as all the patients randomized in the study. The efficacy analysis will be based on FAS. The treatment groups will be compared basis the randomized treatment rather than the actual treatment.
- The per protocol (PP) Set: The Per Protocol analysis set will consist of all patients in the FAS without any major protocol deviation (see section 9.1.1). The PP Analysis Set will be used for sensitivity efficacy analyses.

9.1.3. Patients/Patients disposition

The number and the percentages of patients enrolled and included in each of the populations will be tabulated. The reason for patient exclusions from each of the populations will also be listed. In addition, the number of discontinued patients with their reason for discontinuation will be tabulated.

9.1.4. Demographic and other baseline characteristics

Demographics and other baseline characteristics will be summarized by treatment arm. This analysis will be conducted on the FAS population.

9.1.5. Treatment compliance

Number of daily doses will be presented on the FAS population.

9.2. Safety Analyses

Adverse events will be coded using the standard dictionary (MedDRA) down to the lower level term (LLT).

An overall summary table will be presented (Any adverse event, any treatment emergent adverse event (TEAE), any serious adverse event (SAE) including serious adverse drug reactions (SARs) and suspected unexpected serious adverse reactions (SUSARs), death, any grade 3 or higher adverse events from baseline to the end of Study).

Two periods will be defined for TEAE:

- Any adverse event which occurs or worsens from first dosing to Day 28;
- Any adverse event which occurs after Day 28.

TEAEs will be described by primary system organ class and preferred term. Numbers and percentage of patients, and number of occurrences of adverse event will be presented for:

- TEAE;
- Serious TEAE;
- TEAE leading to study treatment discontinuation;
- TEAE of grade 3 or 4;
- TEAE for which relationship with the study treatment is recorded as possible or probable.

The assessment of safety will be based on the frequency of adverse events (with and without regard to causality) graded according to the CTC-AE Classification (version 5.0) and also, the review of individual values for clinical laboratory data, vital signs and ECG focusing on the detection of abnormal values and PCSAs [potentially clinically significant abnormalities (PCSAs) determined upon investigator considerations].

Clinical laboratory parameters, vital signs, ECG will be summarized by using descriptive statistics (n, mean, SD, median, minimum and maximum). Number of patients with at least one abnormal value will be tabulated (counts and percentages) for each parameter in summary shift tables, by study treatment group.

9.3. Efficacy Analysis

9.3.1. Generalities

Descriptive statistics will be presented by treatment arm for all primary and secondary efficacy variables for each measurement timepoint.

Continuous variables: mean, standard deviation, minimum and maximum and Confidence intervals (CI), median and quartiles will be presented when considered relevant.

Categorical variables: Counts, rates and Confidence intervals (CI) with confidence level appropriately adjusted confidence intervals will be calculated.

Time-to-event variables will be analyzed by Kaplan-Meier plots.

Mixed model analysis of covariance will be conducted on changes from baseline in specifically chosen measurements defined in the SAP. In this model, treatments and visit will be fixed effect, patients will be random effect and baseline values of the respective measurements will be covariates. Other explanatory variables will also be allowed to be included in the model. In order to normalize eventual skewed distributions transformation of the data will also be considered. Study groups will be compared within this model framework.

Additional sensitivity analysis will be performed on PP analysis set.

Additional details will be elaborated in the Statistical Analysis Plan (SAP).

9.3.3. Analysis of Secondary Efficacy Endpoints

The following secondary endpoints will be analyzed. The analysis will be done on FAS population

- Rate of patients hospitalized
- Percentage of patients reporting each severity rating on a 7-point ordinal scale at each study visit (i.e. Not hospitalized, no limitations on activities; Not hospitalized, limitation on activities; Hospitalized, not requiring supplemental oxygen; Hospitalized, requiring supplemental oxygen; Hospitalized, on non-invasive ventilation or high flow oxygen devices; Hospitalized, on invasive mechanical ventilation or ECMO; Death)
- Change in the ranking on an ordinal scale from baseline to days 7, 14, 21, 28, 48 and at 3 months after the last study drug intake
- % change and AUC over time of oxygen saturation measured by daily pulse oximetry before hospitalization
- Rate of patients with SpO₂ ≤94% and rate of patients with SpO₂ ≤92% at Day 28
- Change from enrolment in inflammatory markers in plasma (i.e. MCP-1, MIP-1 α, G-CSF, IL-1b, IL-2, IL-6, IL-7, IL-10, IL-17, INF γ and TNF α) and in immune phenotype and assessment of cell-activation markers in PBMCs at D14, D28 for hospitalized patients only
- Rate of patients requiring oxygen supplementation
- Time to hospitalization (log rank) from baseline
- Time to assisted ventilation and oxygen supplementation (log rank) from baseline
- Number of days of assisted ventilation
- Number of days of oxygen supplementation
- Number of days at the hospital from admission to discharge ps
- Change from baseline in microRNA-124 levels in total blood (PAXgene®) at D0, D7 and
- AUC and % of change from enrolment in CRP, Troponin I & T and D-dimer levels
- Time to death and mortality rate (all causes, and Covid-19 related)
- Time to improvement of one level in the 7-point ordinal scale
- SARS-CoV-2 virus in nasopharyngeal sample and/or in blood at Day 0, 7 (hospitalized patients), 14, 21, and 28
- Change in SpO₂ values from D0 to D14 in the outpatient's population

In addition, exploratory analysis to assess the radiological findings for patients hospitalized because of Covid-19 infection consequences will be performed.

Central blinded review of the hospitalization discharge CT-Scans for descriptive analysis with regards to the disease severity and outcomes.

Additional details will be elaborated in the Statistical Analysis Plan (SAP).

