2.2. Secondary objectives and endpoints

The secondary objectives are:

To evaluate the proportion of patients requiring hospitalization during the study compared to the {Standard of care + placebo} group

- *Rate of patients hospitalized*

To assess the proportion of patients reporting each severity rating on a 7-point ordinal scale during the course of the study compared to the {Standard of care + placebo} group

- *Percentage of patients reporting each severity rating on a 7-point ordinal scale at each study visit (i.e. Not hospitalized, no limitations on activities; Not hospitalized, limitation on activities; Hospitalized, not requiring supplemental oxygen; Hospitalized, requiring supplemental oxygen; Hospitalized, on non-invasive ventilation or high flow oxygen devices; Hospitalized, on invasive mechanical ventilation or ECMO; Death);*

To assess the time to an improvement of one category of the 7-point on an ordinal scale from baseline, compared to the {Standard of care + placebo} groups

- *Change in the ranking on an ordinal scale from baseline to days 7, 14, 21, 28, 48 and at 4 months*

To evaluate and compare the effect of ABX464 on oxygen saturation before hospitalization

- *% change and AUC over time of oxygen saturation measured by daily pulse oximetry before hospitalization*

To evaluate and compare the effect of ABX464 on oxygen saturation level at the end of the study treatment

- *Rate of patients with SpO₂ ≤ 94% and rate of patients with SpO₂ ≤ 92% at Day 28*

To evaluate and compare the effect of ABX464 on immunophenotyping (in selected sites only) and cytokines levels during the study in patients enrolled in both treatment groups.

- *Change from enrolment in inflammatory markers in plasma (i.e. MCP-1, MIP-1 α , G-CSF, IL-1 β , IL-2, IL-6, IL-7, IL-10, IL-17, INF γ and TNF α) and in immune phenotype and assessment of cell-activation markers in PBMCs at D14, D28.*

To evaluate the proportion of patient requiring oxygen supplementation (>3L/min) during the study compared to the {Standard of care + placebo} group.

- *Rate of patients requiring oxygen supplementation*

To assess the time to hospitalization (all causes and Covid-19 related hospitalization) during the study compared to {Standard of care + placebo} treated group.

- *Time to hospitalization from baseline.*

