¹ **Physical examinations:** a complete physical examination will be performed at D0, at the End of treatment visit (EoT), and at D48. Only differences from baseline will be reported at every other visit

² **Body Weight and Height:** Body weight and height will be measured at D0 for BMI assessment.

³ **ECG:** A 12-Leads ECG will be performed at every on-site study visit.

⁴ **Blood pregnancy test:** Applicable to all women of childbearing potential at D0 and at D48. In order not to limit the patient enrollment a urine pregnancy test can be performed in addition if the blood test result is not available at the time of randomization.

⁵ **Hematology + Biochemistry:** samples to be taken at every on-site study visit (except D7 for outpatients if not possible) and analyzed locally.

⁶ **CRP, Troponin I & T and D-Dimer:** samples to be taken at every on-site study visit (except D7 for outpatients if not possible) and sent to central laboratory for biobanking purpose.

⁷ **Immunophenotyping and cells activation markers:** samples will be taken in selected sites and for approximately 100 patients.

⁸ **Blood sample Cytokines:** samples will be taken in all sites for all patients.

⁹ **Chest CT-scan:** procedure concerns hospitalized patients only (whenever the hospitalization occurs during the course of the study). Images taken at discharge (\pm 7 days) will be assessed locally, then collected and sent to a blinded central reader for descriptive analysis of the lesions. If available at D0, Baseline CT scans of hospitalized patients will be sent to Central Reader for comparison purpose.

¹⁰ **Respiratory function evaluation:** This evaluation will be performed only in patients who were hospitalized during the course of the study. For these patients the MRC Dyspnea assessment scale must be used at discharge and 3 months after last study drug intake. For sites having adequate facilities a PFT (FEV₁ and slow and forced Vital Capacity) and a Carbon Monoxide Diffusing Capacity (CMDC) evaluation will be performed at discharge and 3 months after last study drug intake (optional assessments). For this last test, a blood sample for hemoglobin assessment must be taken within 48hrs prior to the CMDC test.

¹¹ **ABX464/placebo treatment dispensation:** treatment dispensation will be allowed once all the selection criteria are confirmed, including laboratory assessments for patients' eligibility confirmation.

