5.2.7. Visit 7 – 3-months follow-up visit (+/- 7 days)

A long-term follow-up will be performed **3 months after the last study drug intake** to explore the respiratory function of patients who have been hospitalized during the study.

Patients having been hospitalized during the course of the study will come back for an on-site visit to perform a respiratory function assessment and a long-term survival evaluation as described below:

- Report the disease severity rating using the 7-point ordinal scale (i.e. Not hospitalized, no limitations on activities; Not hospitalized, limitation on activities; Hospitalized, not requiring supplemental oxygen; Hospitalized, requiring supplemental oxygen; Hospitalized, on non-invasive ventilation or high flow oxygen devices; Hospitalized, on invasive mechanical ventilation or ECMO; Death);
- Evaluation of the dyspnea severity using the Medical Research Council (MRC) Dyspnea scale
- Optional procedures for sites with adequate facilities and resources:
 - PFT (FEV1 and Slow and Forced Vital Capacity)
 - CMDC assessment (optional procedures)
 - Blood sample taken within 48 hours prior the visit for hemoglobin assessment.

For outpatients, mortality status will be collected (phone contact) **3 months after the last study drug intake**.

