5.3.7.3. Lymphocyte Phenotyping, Cytokine Serum Concentrations

Blood and serum samples will be collected at D0 in every site, and then at specified timepoints during the study.

Samples for Immunophenotyping assessment will be taken from selected sites only and for approximately 100 patients, to document effects of ABX464 on T cell, NK and dendritic cell concentrations as well as on cytokines (as described in table 1: Laboratory tests).

Cytokines serum concentrations will be tested in all treated patients at specified timepoints.

These determinations will be performed by a central laboratory.

5.3.8. Volume of blood sampling.

The table 3 below summarizes the volume of blood to be sampled at each study visit. The total (maximal) volume of blood taken from a participating patient is 321 mL to 392 mL (including samples taken during an unscheduled visit).

Table 3: Blood Volume

	D0	D7	D14	D21	D28/EOT	UNSCH	D49	4M FUp
Hematology	2	2	2	2	2	2	2	2
Biochemistry	10	10	10	10	10	10	10	0
Immunophenotyping & cells activation marker	24	0	24	0	24	24	0	0
Cytokines	6	0	6	0	6	6	0	0
miRNA-124	5	5	0	0	5	0	0	0
Viral load	2,5	2,5	2,5	2,5	2,5	2,5	0	0
Plasma (Troponin I & T, CRP, and D-dimer)	17	17	17	17	17	17	0	0
Haemostasis	9	9	9	9	9	9	0	0
TOTAL PER VISIT	75,5	45,5	70,5	40,5	75,5	70,5	12	2

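### Protocol 9.3.3 limits the inflammatory-marker analysis to an undefined hospitalised group, against the rest of the plan, and the 3-month ordinal score is recorded only in patients hospitalised during the study

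*Protocol*

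**What the plan says.** **Analysis population.** Protocol 9.3.3 opens its list of secondary endpoints with "The analysis will be done on FAS population". Section 9.1.2 states that "FAS is defined as all the patients randomized in the study".

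**Markers.** The item in 9.3.3 on change in plasma inflammatory markers, immune phenotype and cell activation ends "cell-activation markers in PBMCs at D14, D28 for hospitalized patients only". The corresponding objective in 2.2 concerns "cytokines levels during the study in patients enrolled in both treatment groups", and the synopsis agrees. Footnote 8 to the flow chart (5.1) says of cytokines that "samples will be taken in all sites for all patients", and 5.3.7.3 adds: "Cytokines serum concentrations will be tested in all treated patients at specified timepoints". Immunophenotyping is different: about 100 patients at selected sites. SAP 4.13 restates the combined endpoint, among those no longer analysed, without a hospitalised-only limit.

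**3-month ordinal scale.** Under the same heading, 9.3.3 lists this endpoint, with the 3 months counted from the final dose: "Change in the ranking on an ordinal scale from baseline to days 7, 14, 21, 28, 48 and at 3 months after the last study". Under 5.2.7, the scale is scored at an on-site visit attended by patients hospitalised during the study. For the rest: "For outpatients, mortality status will be collected (phone contact"). Footnote 12 to the flow chart confirms that the call covers patients not hospitalised during the study.

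**The concern.** Hospitalisation rate and time to hospitalisation are themselves secondary efficacy endpoints. A comparison confined to hospitalised patients is protected by randomisation only if that status was fixed before treatment began. If ABX464 kept the milder cases out of hospital, its remaining hospitalised patients would be sicker on average, and their markers and 3-month status would look worse for that reason alone. If the drug did harm, the distortion would run the other way.

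Cytokine suppression is central to the trial's rationale, so the marker endpoint is an important mechanistic readout. The estimand and missing-data rules in 9.3.2 are written for the primary endpoint, and the protocol gives none for these two comparisons. A reader following 9.3.3 literally would also leave cytokine results outside the hospitalised group without a planned analysis.

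**Working it through.** **1. Three readings of the marker restriction.** The protocol does not say which applies.

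- *Hospitalised at any time, including after randomisation.* The subset depends on a post-randomisation outcome, so selection bias is possible.
- *Inpatient at enrolment.* This is a randomisation stratum (3.1, 6.4). The subset is fixed before treatment and has no selection bias, but outpatient cytokine data have no analysis.
- *The phrase attaches only to the PBMC markers.* It follows that clause directly. Cytokines would then be unrestricted, and the sentence would need rewording to say so.

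Under each reading the text of 9.3.3 has to be reconciled with 2.2, footnote 8 and 5.3.7.3. Where 2.2 intends a limit it states one: selected sites for immunophenotyping, and selected sites and hospitalised patients for miR-124. It states none for cytokines.

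**2. The 3-month score.** Here the documents leave no ambiguity: Visit 7 attendance depends on hospitalisation during the study, which includes admission after randomisation. For everyone else only survival is known. Death (category 7) is captured and categories 1 to 6 are not. A survivor who was never admitted would fall in one of the first two categories, so the gap lies at the favourable end of the scale.

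**3. Illustrative size for the markers, under the first reading.** The plan states no figure for either endpoint. The 78% power in 9.5 is for the primary endpoint and does not enter.

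Assumptions, none documented as such:

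- Hospitalisation is 25% (placebo) and 16% (ABX464). These are borrowed from the primary failure rates in 9.5 (100 − 75 and 100 − 84) and are not hospitalisation rates.
- There are no inpatients at enrolment.
- A patient is hospitalised when a standard normal severity exceeds a threshold a.
- The marker has correlation ρ with severity and no true treatment effect.

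Mean severity among the hospitalised is φ(a)/h, where h is the hospitalised fraction:

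- Placebo, h = 0.25: 1.271 SD
- ABX464, h = 0.16: 1.521 SD
- Gap: 1.521 − 1.271 = 0.25 SD

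The spurious marker difference is ρ × 0.25. Numbers analysed are 267 × 0.25 ≈ 67 and 533 × 0.16 ≈ 85, that is 152 of 800 (19%). The standard error relative to analysing everyone is √(1/66.75 + 1/85.28) / √(1/267 + 1/533) = 2.18.

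| ρ | Spurious difference, 25% vs 16% | Two-sided false-positive rate at nominal 5% | Spurious difference, 40% vs 30% |
|---|---|---|---|
| 0.3 | 0.075 SD | 7.6% | 0.058 SD |
| 0.5 | 0.125 SD | 13.6% | 0.097 SD |
| 0.7 | 0.175 SD | 27.4% | 0.135 SD |

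With equal hospitalisation (25% in both arms) the difference is 0 and the error rate stays at 5%.

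**4. Effect of baseline inpatients.** They are hospitalised whatever their treatment, so they dilute the bias. Suppose 25% of patients are inpatients at enrolment, 25% vs 16% of the outpatients are later admitted, and the two strata are pooled with weights nₚnₐ/(nₚ + nₐ), where p and a denote placebo and ABX464.

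- Inpatients: 66.75 × 133.25 / 200 = 44.5
- Later admissions: 50.06 × 63.96 / 114.02 = 28.1
- Share of weight carrying the bias: 28.1 / 72.6 = 0.39

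The bias falls to about 0.03, 0.05 and 0.07 SD and the standard-error ratio to 1.6. With a 50% inpatient share the same steps give about 0.01, 0.02 and 0.03 SD and 1.3.

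**The case against.** The strongest reply is that one stray phrase in 9.3.3 stands against the synopsis, 2.2, footnote 8, 5.3.7.3, the opening of 9.3.3 itself and SAP 4.13. On that view it is a drafting slip and not a deliberate choice of population. The quoted words also name PBMC markers, which are taken in only about 100 patients. Both points stand, and they are why no single reading can be asserted.

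Three stronger conclusions that a reader might infer are not supported:

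- *That the marker comparison certainly conditions on a post-randomisation outcome.* It may refer to the enrolment stratum.
- *That most of the cytokine data would be discarded.* No document gives the inpatient share.
- *That the bias is known to be 0.075 to 0.175 SD.* Those figures rest on borrowed rates and no baseline inpatients. They also model a marker level, whereas the endpoint is change from enrolment, whose correlation with admission is a different and unstated quantity.

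The 3-month gap is narrow: it is one of six listed timepoints, the day 7 to 48 scores do not use this visit, and deaths are still captured. What survives is that 9.3.3 read literally would narrow the marker analysis for no stated reason, and that the 3-month score cannot be analysed on all randomised patients with the data the plan collects.

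**Conclusion.** The point holds as an internal conflict in the protocol with a plausible route to bias. For the 3-month ordinal score, dependence on a post-randomisation outcome is certain from the text. For the markers it is one of three possible readings. Any numerical size is illustrative: up to 0.175 SD against ABX464 under the stated assumptions, less with baseline inpatients, and zero with equal hospitalisation.

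These are secondary endpoints, 9.6 gives no multiplicity scheme, and the primary endpoint is untouched. SAP version 5.0 dropped all efficacy analyses after the futility stop, so no currently planned result changes. The point concerns the protocol's design, and it would matter again if the stored samples were analysed later.

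**What to change.** In 9.3.3, delete the closing hospitalised-only qualifier for plasma cytokines. Analyse all sampled patients in the full analysis set, adjusted for baseline value and the randomisation strata. For the PBMC markers, analyse everyone in the sampled subset. Keep any hospitalised-only summary descriptive, and define the term.

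For the ordinal scale, record the category at the existing 3-month call for patients never hospitalised. For a survivor this comes down mainly to whether activities are limited. Failing that, label the 3-month ordinal result as descriptive in patients ever hospitalised, and remove it from the analyses listed on all randomised patients.

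The cost is a wording change, one extra item in a scheduled call, and cytokine assays that 5.3.7.3 already says will be done.
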